NCT03168867

Effectiveness Trial of an E-Health Intervention To Support Diabetes Care in Minority Youth (3Ms) 3/20/23

Study Protocol with Statistical Analysis Plan

The effectiveness trial is a multi-site clinical trial using a randomized, controlled, repeated measures design to test the effects of a computer delivered eHealth parenting intervention to improve health outcomes among African American adolescents with type 1 diabetes (T1D). The study will be conducted at 3 clinics in the Detroit area and 4 clinics in the Chicago area. 212 African American (AA) adolescents with type 1 diabetes and their primary caregivers will be enrolled. Study consent and the baseline assessment session will be completed in the diabetes clinic at the time of a regularly scheduled medical appointment Families will be randomized to one of two arms: *The 3Ms* intervention (to increase parental motivation for monitoring of adolescent DSM) or *standard control*. Participants will be allocated to the treatment arm using block randomization within 8 strata defined by the four sites and HbA1c level (most recent HbA1c ≤9.5% vs. >9.5%). Within these strata, the software will randomly assign participants to conditions in a 1:1 ratio to ensure equivalence in each condition.

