Parents will complete the first intervention session in the diabetes clinic immediately after baseline data collection and randomization. The subsequent two intervention sessions will also be conducted during regularly scheduled diabetes clinic visits and can be completed any time in the 12-month window after baseline assessment. American Diabetes Association standards of care for youth with diabetes specify that visits to a diabetes specialty care center should occur quarterly; therefore, participants should be seen in clinic four times in a 12-month window. *The 3Ms* intervention is designed to be delivered over nine months should families receive diabetes care at the recommended frequency. Data collection will occur on a different schedule than intervention sessions and will occur at regularly scheduled visits conducted at six months and 12 months after baseline data collection. It is also important to note that while the 12-month data collection visit will typically occur 12 months from baseline, it must also occur at least 30 days from the date of the last intervention session (so that any changes in HbA1c occurring as a result of the intervention can be detected). The data analyses to be used in the study can accommodate varying lengths of time between data collection sessions. A final data collection session will be conducted 18 months after baseline to assess stability of intervention effects in the 6 months after intervention completion.

Participants will be 212 African American adolescents aged 10 years, 0 months -13 years 11 months diagnosed with T1D for a minimum of six months, and their parents. Given that this is an effectiveness trial, exclusion criteria are kept to a minimum so that transportability to real-world settings is adequately assessed. No exclusions will be made due to co-morbid mental health problems (e.g. ADHD, conduct disorder, depression), with the exception of schizophrenia/other psychosis, current suicidality or homicidality. Adolescents with cognitive impairments are also excluded if those impairments are severe enough to result in inability to complete research measures or impact their independence with diabetes care. Finally, if potential subjects have diabetes secondary to another chronic medical illness (e.g. cystic fibrosis) and their medical management differs substantially from that of most children with type 1 diabetes, they will be excluded.

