All measures will be administered at baseline, 6, 12 and 18 months. The primary outcome glycemic control will be measured via hemoglobin A1c (HbA1c). HbA1c will be obtained using the Accubase A1c test kit manufactured by Diabetes Technologies. The Accubase test is FDA approved and uses a capillary tube blood collection method instead of venipuncture. It is therefore suitable for home-based data collection. High performance liquid chromatography (HPLC) is used to analyze the blood sample. Samples are stable for up to 30 days unrefrigerated and vials are bar coded to ensure confidentiality but minimize the likelihood of data loss. Secondary outcomes are measures by questionnaire self-report and/ or parent report.

In the preliminary study, the pooled standard deviation estimate for HbA1c change was 1.34%. If a sample size for the planned analyses is approximated by a t-test for the change in HbA1c from baseline to 12 or 18 months, a sample size of 97 per study arm will allow difference of 0.6% in HbA1c (based on our pilot data and the clinical significance of a 0.5% change), to be detected with 80% power (alpha = 0.025). If 106 families are enrolled per arm, a net sample size of 97 allows for 8% subject attrition/loss to follow-up. Our retention rates in our pilot study were 94%. A sample of this size is also sufficient to identify moderator variables that account for 7% increment in outcome variance using moderated regression analysis. Since outcome data will be collected during home visits, and even patients with incomplete data will contribute to the effective net sample size, the planned sample size is considered feasible with a total of 212 participants enrolled (106 3Ms, 106 control).

The primary outcome will be analyzed using the linear mixed effect model (LME) for repeated measures. Contrasts on the repeated measures [baseline minus 6-month, baseline minus 12-month (end of treatment), and baseline minus 18-month (6-month follow-up)] will partition the main effect of time. Three single degree of freedom contrasts will be defined by crossing the treatment arm factor with each time contrast; the latter two contrasts will test the primary hypotheses at intervention completion and six-month follow-up. The analysis will

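### The 12- and 18-month contrasts are both primary and sized at alpha 0.025, but no testing rule is stated; Holm at two-sided 0.05 would improve on a fixed split at no cost in patients

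*Combined protocol and SAP*

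**What the plan says.** The paragraph on analysis of the primary outcome describes a linear mixed model with three treatment-by-time contrasts, at 6, 12 and 18 months. Of these, "the latter two contrasts will test the primary hypotheses at intervention completion and six-month follow-up". Neither contrast is ranked above the other.

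The sample-size paragraph is the only place where a significance level appears. It says that "a sample size of 97 per study arm will allow difference of 0.6% in HbA1c", "to be detected with 80% power (alpha = 0.025". The test is "approximated by a t-test for the change in HbA1c from baseline to 12 or 18 months", and sidedness is not given.

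The analysis text goes on to intention-to-treat, covariates and moderators. It states no level for the primary tests, no sidedness, no multiplicity procedure and no order. It does not say whether success means either contrast or both.

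The data-collection schedule describes the 18-month visit as held "to assess stability of intervention effects in the 6 months after intervention completion".

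**The concern.** The trial's main claim rests on two tests, and the text does not say how their p-values become a conclusion. Suppose one contrast gives p = 0.01 and the other p = 0.04:

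- With a fixed 0.025 per contrast, an effect is claimed at one time point.
- With Holm at 0.05, it is claimed at both.
- If both contrasts are required, each at 0.05, the trial succeeds.
- If both are required, each at 0.025, it fails.

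Left unwritten, that choice can be made after the results are known.

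There is also a question of efficiency. If the sizing level is simply carried into the analysis, the rule is a plain Bonferroni split. For two unordered hypotheses Holm is never less powerful than that split and controls the same error rate.

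**Working it through.** **Inputs from the documents.** Difference 0.6 and SD of change 1.34 (percentage points of HbA1c), power 80%, alpha 0.025, allocation 1:1, 97 per arm net of attrition, two primary contrasts.

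**Assumptions not in the documents.** The correlation between the 12- and 18-month test statistics is taken as 0.5 to 0.7. Both contrasts share the baseline value, so a positive correlation is expected. Power at 12 months is set at 80% at two-sided 0.025.

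**Step 1: reproduce the 97.** The normal approximation is n per arm = 2 (SD/d)² (z₁₋α/₂ + z₀.₈)², with (1.34/0.6)² = 4.988.

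- Two-sided 0.025: 2 × 4.988 × (2.241 + 0.842)² = 94.8, so 95. The non-central t gives 97, with power 80.4%.
- Two-sided 0.05 (or, equivalently here, one-sided 0.025): 2 × 4.988 × (1.960 + 0.842)² = 78.3, so 79. The non-central t gives 80.

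Only two-sided 0.025 returns 97. Since 0.025 + 0.025 = 0.05, this matches 0.05 split equally over the two primary contrasts.

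**Step 2: set up the comparison.** Take two jointly normal test statistics. The mean for the full effect is z₀.₉₈₇₅ + z₀.₈ = 2.241 + 0.842 = 3.083. Fixed 0.025 rejects a contrast when |z| > 2.241. Holm does the same and, once one contrast has passed, tests the other at |z| > 1.960. Results are from simulation, 4 million draws per case.

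**Step 3: equal effect at both times.**

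| Power (%) at correlation 0.5 / 0.7 | Fixed 0.025 | Holm at 0.05 |
|---|---|---|
| Each contrast | 80.0 / 80.0 | 84.6 / 84.1 |
| Both contrasts | 68.7 / 71.3 | 77.9 / 79.4 |
| At least one | 91.3 / 88.7 | 91.3 / 88.7 |

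Two checks by hand at correlation 0.5:

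- At least one = 80.0 + 80.0 − 68.7 = 91.3.
- By symmetry, Holm's gain for both is twice its gain per contrast: (77.9 − 68.7)/2 = 4.6, and 80.0 + 4.6 = 84.6.

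Over correlations 0.3 to 0.8, Holm gives 85.0 to 83.7% per contrast and 76.6 to 80.4% for both. Fixed 0.025 gives 66.6 to 72.9% for both.

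**Step 4: effect fading to three quarters at 18 months** (0.75 × 0.6 = 0.45; mean 0.75 × 3.083 = 2.312).

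| Power (%) at correlation 0.5 / 0.7 | Fixed 0.025 | Holm at 0.05 | Fixed sequence, 12 then 18, each at 0.05 |
|---|---|---|---|
| 12 months | 80.0 / 80.0 | 82.2 / 81.4 | 86.9 / 86.9 |
| 18 months | 52.8 / 52.8 | 61.6 / 62.0 | 59.8 / 61.7 |

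**Step 5: family-wise error with no effect at either time.** Fixed 0.025 and Holm both give 4.6 / 4.3%. Holm's 5% limit holds whatever the correlation. For orientation only, testing each contrast at 0.05 with either one sufficing would give 9.1 / 8.3%; the documents do not say this would be done.

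**The case against.** The strongest reply is that error control is already in the plan. The value 0.025 is written down, in a sentence about the "change in HbA1c from baseline to 12 or 18 months", and exactly two primary contrasts follow. A reader would naturally carry 0.025 into each test, and that rule is valid. On this view only a clarifying sentence is missing and Holm is a preference. Much of this stands: the level is stated, and only its two-sidedness and its origin as a split are inferred. Even so, an alpha in a sizing approximation is not a decision rule, and it does not say whether one or both contrasts must succeed.

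A second reply is that the stability language for 18 months suits a fixed sequence at least as well. In the fading case the fixed sequence gains about 5 points over Holm at 12 months and loses at most 2 at 18. That is a fair comparison. But a fixed sequence needs an order, which the analysis text does not give, and it bars any 18-month claim when 12 months fails. Splitting alpha, as the sizing appears to do, makes sense only if either contrast may succeed on its own.

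Third, the document is dated 3/20/23 and does not say whether outcomes have been seen by arm. Moving to Holm after that would make some p-values between 0.025 and 0.05 significant. This limits when the change can be made; it does not count against the method.

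Finally, Holm does not raise the chance of at least one significant contrast, and its decisions do not match simple 97.5% intervals exactly. Both points stand.

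**Conclusion.** The concern holds. The plan has two unordered primary contrasts, a sizing that implies two-sided 0.025 for each, and no testing rule. This is an omission plus a missed improvement, not an error in the sample size, and the plan should be corrected. The essential part is to state the level, the sidedness and what counts as success. Holm is the recommended rule if either contrast may succeed. At correlation 0.5 to 0.7 it adds 4 to 5 points of power per contrast and 8 to 9 points for both. If the effect fades by a quarter, it adds about 9 points at 18 months. These gains rest on the assumed correlation and effect pattern. Holm's validity, and the fact that it never rejects less than fixed 0.025, do not.

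**What to change.** Provided outcome data have not been seen by arm, add to the primary-outcome analysis text:

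> An effect may be claimed at 12 months, at 18 months, or at both. The two treatment-by-time contrasts are tested by the Holm procedure at a two-sided family-wise alpha of 0.05: the smaller p-value is compared with 0.025 and, if it is significant, the other is compared with 0.05.

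In the sample-size paragraph, mark the 0.025 as two-sided.

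If the team means something else, it should say so:

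- **Both contrasts required:** test each at two-sided 0.05. Power for both is 79–80% with equal effects, and Holm is not needed.
- **18 months only as maintenance of a 12-month effect:** test 12 months and then 18, each at 0.05. Power with equal effects is 87% at 12 months and 79–80% at 18, with no 18-month claim if 12 months fails.

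If outcomes have already been seen by arm, stating a fixed two-sided 0.025 per contrast is safer, because that is the level already on paper.

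The cost is two sentences and one word, with no change in sample size. The one drawback is that simple 97.5% confidence intervals will not correspond exactly to the Holm decisions.
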